We will measure alcohol-related consequences present at baseline and at 3-month follow-up, as measured by the SIP. The intervention is designed and hypothesized to reduce the quantity and frequency of risky drinking, which can be logically expected to lead to reduced frequency of consequences associated with drinking. However, the Relational Agent is not specifically designed to reduce these consequences, and the relatively short (3-month) follow-up period is not likely to be sufficient to demonstrate a differential rate of consequences between the treatment groups; as a result, data on consequences will be collected for exploration and hypothesis generation for future studies, rather than a priori formal outcome measures. The consequences will be ascertained by means of the SIP. The SIP will be administered at the baseline and 3-month interviews.

In addition, we will measure Veterans' satisfaction with treatment for alcohol problems. To our knowledge, there exists no scale or question designed specifically to measure patients' satisfaction with the care they received for alcohol problems in primary care. Prior studies have used various questions and scales to assess clients' satisfaction with mental health or substance abuse treatment and the Consumer Assessment of Healthcare Providers and Systems (CAHPS) has emerged as a standard for measuring satisfaction with health care delivery, including primary care. We will use a single item, modeled on CAHPS, to assess satisfaction: "On a 0 to 10 point scale, with 0 being the worst care you can imagine and 10 being the best care you can imagine, how would you rate the care you have received in the last 3 months from the VA for alcohol problems?"

Descriptor Variables

[figure not shown]
We will collect data at baseline for the purpose of describing the sample and also analyzing potential moderating variables (i.e., covariates). This information will include age, educational level, race/ethnicity, branch of service, location of deployment, if any, and months of deployment. We will ask about substance

abuse treatment in the last 12 months. We will also collect the following information from CPRS: mental health diagnoses, especially post-traumatic stress disorder (PTSD); and diagnosis of traumatic brain injury (TBI). It is unknown if these variables affect outcomes for brief intervention, and thus a fruitful area for exploratory analyses.

Other variables that we will use to describe the sample and explore in cross-tabulations with the outcome variables include summary scores from the REALM health literacy questions and .the ECA Questionnaire.

Statistical Analysis

The figure below shows a schematic representation of the research design. For visual clarity, it does not show the descriptive variables mentioned above.

Preliminary Analyses: In preliminary analyses, we will examine the distributions of all dependent variables, and consider appropriate transformations. In particular, we will consider an arcsine transformation (appropriate for reported proportions) for the “number of drinking days per week” and a log transformation (appropriate for highly skewed distributions) for “average drinks per drinking day”. The 4 groups will be tested for any differences in socio-demographic variables. All quantitative variables (e.g. Age) will be tested by 2-way between groups Analysis of Variance (ANOVA); all qualitative variables (e.g. Gender) will be tested by 3-dimensional Chi Square (Mantel-Haenszel test). Any variable found to be significant will be entered into all subsequent analyses as a covariate.

Checks for “non-Response” Bias: The potential for differential drop-out rates among the four groups is itself an interesting and important empirical question, with clinical implications. Drop-out rates will be tested by Chi Square. Factors that may contribute to drop-out rate will be tested by logistic regression. In effect, the four groups can be stratified at Baseline into Completers and non-Completers. Then, these groups will be compared on Baseline values to determine which, if any, are significant systematic “predictors” of Completion.

Statistical Analyses: If there is no significant differential drop-out rate attributable to Alcohol Group, to Treatment Group, or, especially, to Alcohol x Treatment interaction, then the non-completion rate can be considered as a random loss, and Completers as a representative sample. In that case, the dependent variable(s) will be tested by 3-way mixed design AN(CO)VA. If it is determined that there is a differential drop-out rate such that the data are not missing completely at random (NMCAR), then we will utilize a generalized estimation equation (GEE) approach, which should provide an unbiased estimate of the intervention effect.

GEE utilizes inverse probabilities to correct for any bias associated with NMCAR, with participants who are Completers weighted with the drop-out probabilities of participants with the “same” characteristics at Baseline. These weighting values will be estimated from the logistic analyses described above.

The overall design is a three-way mixed-design with Treatment Arm (Treatment as Usual vs. Treatment as Usual plus Relational Agent Intervention) and Drinking Severity (Risky vs. Alcohol Use Disorder) and 2 occasions (0 and 3 months) as the repeated measures design. We will take an intent-to-treat approach to the analysis; Veterans will be included in our primary analyses regardless of their level of adherence with their assigned intervention. Participants who do not complete the 3-month follow-up assessment will be considered to have missing data for that assessment and will not be included in the analysis of intervention effectiveness. The secondary outcomes, which will be “incidence rates”, will be tested by logistic regression.

Primary Hypothesis: The Relational Agent will be more effective than Treatment as Usual in reducing the quantity and frequency of alcohol use.

Our primary analyses of the effectiveness of Treatment as Usual vs. Treatment as Usual plus Relational Agent Intervention will focus on measurement outcome variables at the **3-month follow-up**. Separate analyses will be performed for the two primary outcome measures: number of drinking days per week (frequency) and average drinks per drinking day (quantity), both reported over a month. Here we describe the analytic approach for the outcome of quantity of alcohol use (average drinks per drinking day); the approach for frequency will be analogous. Initially our analysis will be through analysis of covariance models. We will include baseline values of the outcome variable as a covariate in these models, so our analyses may be interpreted as focusing on the change in outcome from baseline to three month follow-up. If any key characteristics of our sample were found to differ between groups, we will enter those as covariates as well.

Secondary Hypothesis: The Relational Agent will be more effective than Treatment as Usual in improving rates of brief intervention.

For our secondary outcome of increased rate of delivering brief intervention, we will compare the two study groups on the proportion of patients receiving brief intervention through the chi-square test. Logistic regression will be used to calculate odds ratios and 95% confidence intervals in order to describe differences in rates of brief intervention between groups. To further examine baseline patient characteristics that predict brief intervention, and control for any covariates found to differ between treatment groups at baseline, we will develop a multivariable logistic regression model predicting rate of brief intervention from baseline characteristics as well as indicator variables representing the intervention group and presence/absence of alcohol use disorders.

Secondary Hypothesis: The Relational Agent will be more effective than Treatment as Usual in improving rates of referral to specialty treatment.

Secondary analysis also includes a comparison of referral rates, and analyses similar to those described for the secondary Hypothesis above will be employed. We will compare study groups on the proportion of patients referred through the chi-square test. Since we expect that Veterans with alcohol use disorders will be more likely to be referred regardless of group, we will test this hypothesis separately, i.e., we will use chi-square to compare rates of referral based solely on presence or absence of alcohol use disorders. Logistic regression will be used to calculate odds ratios and 95% confidence intervals in order to describe differences in referral rates between groups. To further examine baseline patient characteristics that predict brief intervention, and control for any covariates found to differ between treatment groups at baseline, we will develop a multivariable logistic regression model predicting referral rates from baseline characteristics as well as indicator variables representing the intervention group and presence/absence of alcohol use disorders.

Additional exploratory hypotheses:

Negative consequences for alcohol use, as measured by the SIP, may also decrease as a result of intervention, and this hypothesis will be explored as well through a random effects linear regression model.

Sample Size and Power Considerations

Power considerations focus on our primary hypotheses, which examine intervention effects on two primary outcomes, drinking days per week and average drinks per drinking day, at 3 months follow-up. For our principal analyses we will separately examine effects on these outcomes at 3 months through analysis of covariance, controlling for baseline levels of the outcome variable. Reported effects of brief intervention vary in the literature.

For instance, a meta-analysis by Moyer et al. found an effect size for alcohol consumption in non-treatment-seeking samples of 0.67 for drinks per day at three months, but it quickly drops to 0.14 at six months, and 0.24 at 12 months.⁹⁵ On the other hand, Bien et al. reported an average effect size of 0.64 at 12 months for the reduction in drinks per month, but it varied in studies they reviewed from 0.27 to over 1.0.¹⁷ More to the point for our study, Riper et al.⁹⁶ conducted a meta-analysis of web-based brief interventions and reported a medium effect size ($d=0.44$). There are little data to suggest that those with alcohol use disorders derive more or less benefit from brief intervention.³³ However, VA clinical guidelines suggest that people with alcohol use disorders need to be referred to specialty treatment, implying that they might not be expected to benefit solely from brief intervention. With these prior studies in mind, and with the explicit design of this study as an initial, single-site RCT to assess the potential effectiveness of the Relational Agent Intervention on frequency and quantity of alcohol use among Veterans, we have powered the trial for the detection of a large effect size, as defined by Cohen.⁹⁷

We begin our sample size estimation with the observation that 5,571 underwent AUD-C screening in our study setting during fiscal year 2010. We estimate that $1.25 * 5,571 = 6,963$ will be screened during the **15-month** study enrollment period. National samples indicate that about 20% of Veterans screened receive a positive score on the AUD-C,²⁶ which would be consistent with the estimated prevalence in the larger population. Therefore, $6,963 * 0.2 = 1,393$ Veterans will be potentially eligible. Because of clinic workflow and research assistant availability, we anticipate approaching approximately **500** of these Veterans. Based on [name] pilot study of a Relational Agent to screen for alcohol problems in primary care (described above, Section 4.a.1) and the two recently completed pilot studies of the Relational Agent in the Primary Care Clinic of VA Boston, we estimate that **36% of the 500** Veterans approached, or **180** Veterans, will agree to participate. We estimate that these **180** Veterans will be distributed in a 2:1 ratio as those with alcohol use disorders ($N=120$) and those with risky drinking ($N=60$), based on studies in VA.

Rates of attrition, or loss-to-follow-up, in prior studies of brief intervention for alcohol problems have typically ranged from 10% to 30%. Based on our familiarity with following up study participants in alcohol and substance abuse interventions, and particularly noting our use of financial compensation for participation, we anticipate that our loss-to-follow-up will be on the lower end of this range. However, in the table below we show power estimates for three possible rates of loss to follow-up: 20%, 25% and 30%. Table 5 shows estimated power to detect a **medium (Cohen's) effect size**, at an alpha level of 0.05, given the three possible rates of loss-to-follow-up.

Power estimates for a range of loss-to-follow-up rates

% Loss-to-Follow-Up	Experimental Group	Alcohol Use Disorders (N)	Risky Drinking (N)	Total (N)	Power
20%	TAU	48	24	72	0.84
	TAU+RAI	48	24	72	
25%	TAU	45	22.5	68	0.82
	TAU+RAI	45	22.5	68	
30%	TAU	42	21	63	0.78
	TAU+RAI	42	21	63	

Note: TAU=Treatment as Usual; RAI=Relational Agent Intervention.

Thus, for our primary outcome, we estimate that we will have more than 80% power to detect a medium effect of the intervention with loss-to-follow-up rates approaching 30%. We will monitor loss-to-follow-up closely and, if we discover that the attrition rate is exceeding 30%, we will increase our sample size to account for the loss-to-follow-up.

We will recruit a total of **180** Veterans from PCC, with approximately **60** participants in the Risky Drinking Group and **120** participants in the Alcohol Use Disorders Group. Accounting for 20-30% loss to follow up we expect that at least **126 to 144** Veterans will complete the 3-month follow-up.

Specific Aim 3: Examine in-depth Veterans' experience with the Relational Agent Intervention.

Because this Aim is exploratory in nature, there are no associated hypotheses. Following the RCT, we will conduct a formative evaluation (Aim 3), with in-depth interviews, to characterize the elements of the Relational Agent Intervention that Veterans prefer, and the features that emerge as most effective and those that seem extraneous or even counter-productive.

Rationale for formative evaluation

Formative evaluation will inform future evaluation and implementation efforts, specifically in the area of Relational Agents for alcohol problems and more generically for interventions using health information technology to engage Veterans in their care in the primary care setting. Formative evaluation is valuable in the context of an intervention that results in quantitative improvement of outcomes because it can yield information regarding those characteristics of the intervention that seemed most useful and effective from the perspective of the study participants. Perhaps more importantly, formative evaluation is crucial in the context of an intervention that does not result in quantitative improvement in the target outcome (i.e., in the setting of a "negative study"), because it can identify the factors that may have prevented an otherwise-potent intervention from achieving the intended outcome.

In-depth Interviews

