Following the baseline interview and stratification, the research assistant will randomize Veterans to Treatment as Usual or Treatment as Usual plus Relational Agent Intervention. As described above, Veterans will be stratified by the severity of alcohol use disorder. Within strata, block randomization with variable block sizes will be used to ensure that treatment groups balance over time. The block sizes will be randomly varied and of sufficient size to minimize the ability of any study staff or Veterans to guess the next random allocation assignment. Randomization assignments will be generated using computer-generated random numbers and will be available immediately to the research assistant upon entering the Veteran-participant's information and responses from the baseline interview. We will use the randomization procedure available in RedCAP. After the research assistant determines the random allocation assignment of the Veteran-participant, the Veteran will be directed either to proceed to his scheduled clinical encounter (Treatment as Usual) or will be introduced to the Relational Agent Intervention.

Relational Agent Intervention-procedure

When a Veteran is allocated to Relational Agent + Treatment as Usual, the research assistant will first enroll the participant into the Relational Agent system (entering the participant's ID, gender, given name, and presence/absence of AUD), introduce the Veteran to the Relational Agent, explain briefly how the Relational Agent works, then allow the Veteran to complete the Relational Agent program in privacy using headphones.

We are using AUDIT scores and previous substance abuse treatment in addition to the MINI as conservative indicators of the need for specialty treatment. Negative results on these measures will result in a brief intervention only. A positive result for alcohol abuse or dependence from the MINI during the baseline assessment, previous substance abuse treatment, or a score higher than 20 on the AUDIT will trigger a referral to specialty treatment at the end of the intervention.

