When session 1 is over, the research assistant will print out the patient feedback report for the participant, and make sure they are scheduled for session 2 and the 3 month research interview. The patient feedback report will contain information about the participant's drinking and their list of pros and cons (see Appendix B). The clinic report will contain information about the participant's drinking, and whether or not a referral was agreed upon. The information from the clinic report will go into a progress note in CPRS, and will be

used for referral if needed. The research assistant will check the clinic report to see if a referral is indicated, and contact [name] or [name] if a consult (referral) is indicated. [name] or [name] will speak with the participant on the phone to gather information for the consult and place the consult for the participant. If, in the unlikely event that either [name] or [name] are not available, the research assistant will contact the postdoctoral fellow working on this project, or walk the participant down to the offices of the Primary Care Mental Health staff for assistance. If there are any concerns about suicidality or homicidality from the telephone consult process, the research assistant will walk the participant over to Primary Care Mental Health staff for assistance. If they are not available the research assistant will alert the primary care team and hand off the patient to one of the PCC staff who can bring the patient to urgent care. See “Human Subjects – Protection Against Risk” for more detail.

When the participant returns for session 2, the research assistant will again set up the computer for the participant and allow them to use the program in privacy, using headphones. At the end of the session, the research assistant will print out the patient feedback report, confirm the 3 month follow-up appointment, and check the clinic report for instructions. If a referral is needed the research assistant will follow the same procedure as above. Veterans receive \$10 in for completing questionnaires after session 2.

The research assistant will also ask the Veteran to fill out the System Usability Scale and the ECA Questionnaire.

Three-Month Follow-up Interview

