The research assistants will conduct the 3-month follow-up interview by telephone with each enrolled study participant. Each of these telephone interviews will take approximately 15 minutes and will include completion of the QDS and SIP. The research assistant will also ask whether the Veteran received brief intervention or referral for alcohol problems at the index primary care visit or in the intervening 3-month period; this ascertainment will complement the documentation of brief intervention and referral that may be present in the computerized patient record system (CPRS). In addition, the research assistant will ask about Veterans’ satisfaction with care for alcohol problems in PCC. Veterans receive \$20 in appreciation for their participation in completing the 3 month follow-up interview.

Follow-up Procedures

To minimize loss-to-follow-up and maximize participation, we will send each participant a reminder letter approximately one week prior to each interview. We also leave a reminder call a few days before. [name] will train the research assistants to conduct the in-person and 3 month telephone interviews and will monitor their quality and accuracy. The research assistants will follow a written protocol for conducting these calls, including a script (see Appendix B) for how to interact with automated telephone answering systems (machines or voice mail) and how to confirm the identity of the Veteran to ensure privacy and confidentiality. Based on our prior studies, we developed a protocol for multiple call attempts if the Veteran is unreachable, followed by up to 3 letters attempting to reschedule the missed appointments. If we are still unable to contact the participants we will send out the locator letters and follow them up with a phone call to the locator person(s). We will also check CPRS for changes in phone numbers or addresses, and to check if a participant is scheduled for a visit in the near future where we can speak with them. Data from each of these interviews will be entered into RedCAP on a study laptop computer (equipped with all required encryption and passwords) and eventually converted to Statistical Package for the Social Sciences Software (SPSS) data file format for statistical analysis.

Review of the Computerized Patient Record System (CPRS)

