Data collection and storage. Research interviews and other relevant data will be collected via the REDCap program behind the VA firewall and stored on a VA server. REDCap allows the assignment of different levels of access privileges and audit trails, thus ensuring proper data management and minimizing mistakes. For instance the Project Manager can be the only one who is allowed to edit data, while RAs can be allowed to enter and download data only. At the time of this IRB amendment (2/9/16), we were given permission to use REDCap while it is under review for VA Research by VACO. If REDCap is disallowed, we will identify and propose alternative systems.

The Relational Agent software is installed on VA tablet/laptops and the database for the program will be on a VA server. The software installed on the tablets includes custom software created by Northeastern University computer scientists, Unity software used for animation, and XXAMP, a web application. Also, the system uses MySQL database on both the tablets and the VA server. It is installed on the tablets for local storage, and as insurance against being unable to run the program if wifi connection is unavailable. It gets backed up to the VA servers. Both the database on tablets and VA server and the transmission to the server can be encrypted.

Study Design for Aim 2

This study is a mixed design, with Alcohol Severity Groups and Treatment Arms as between-groups variables and Time of Testing (Baseline vs. 3-Month Follow-up) as a repeated measure variable. The main focus of this initial RCT is to compare Treatment as Usual (TAU) to TAU plus the Relational Agent Intervention

(TAU+RA) on (a) alcohol consumption, (b) rates of brief intervention, and (c) rates of referral to treatment. We will use a stratified randomization scheme, stratifying on whether a Veteran is a risky drinker or has the more severe designation of an alcohol use disorder, to ensure that the two study groups balance on severity. Veterans allocated to Treatment as Usual will continue to receive all usual care as delivered in the PCC. Veterans allocated to Treatment as Usual plus Relational Agent Intervention will interact with the Relational Agent as soon as possible following the baseline assessment, and still receive usual care.

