Alcohol use and related behaviors will be assessed by in-person survey at baseline and by telephone survey at 3 months after randomization. Principal intervention effect analyses will be performed at 3 months. The primary dependent (outcome) variables are number of drinking days per week (frequency) and average drinks per drinking day (quantity). Secondary dependent variables are percent receiving brief intervention and percent referred for further evaluation or treatment of alcohol problems.

Independent Variables

The two independent variables are the experimental condition, Treatment as Usual vs. Treatment as Usual plus Relational Agent Intervention, and the severity of alcohol use, dichotomized as Risky Drinking vs. Alcohol Use Disorder. The experimental condition will be assigned by random allocation (see Section 4.e.7).

The severity of alcohol use variable, which will be used to allocate Veteran-participants into two strata prior to randomization, will be ascertained by the baseline completion of the MINI.

Dependent Variables

The primary dependent variables (i.e., the main study outcome measures) are **number of drinking days per week** and **average drinks per drinking day**. Because the Relational Agent will target reduction of both the frequency (number of drinking days per week) and the quantity (average drinks per drinking day) of alcohol consumption, each of these measures will be considered separately as primary outcome measures. These variables are measured by the QDS.

Secondary dependent variables include **completion of brief intervention** (yes/no) and **referral for evaluation/treatment** (yes/no); these secondary dependent variables will be ascertained from review of CPRS. We will also ascertain completion of brief intervention and referral for evaluation/treatment from the interviews with participants; we will assess concordance between CPRS and Veterans' self-report and, for main analyses, we will count brief intervention or referral as completed if they are ascertained from either source.

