Clinic staff administer the AUD-C once a year to all Veterans. If a Veteran scores above the cutoff, clinic staff will inform the Veteran about the study and ask them to sign the "permission to contact" form if they are interested. This form will be passed on to the Research Assistant, who will meet with the Veteran to conduct the screening. The RA will briefly explain what the study is about and ask if the Veteran will have a stable phone number and address for the next 6 months. If the answer is yes, the research assistant will administer the Quick Drinking Screen (quantity and frequency of drinking in the past 30 days). If the Veteran is drinking above CDC guidelines, additional screening questions will be administered. If the Veteran is eligible, the consent form will be read to the participant. The RA will stop after each page or each section of the ICF and ask if the veteran understands or has any questions. Once the ICF has been signed, the RA will ask about substance Abuse treatment in the last month. If the veteran has not had treatment in the last month, the RA administer baseline questionnaires, randomize the participant, and inform the participant of their assignment, and an appointment for the 3 month follow up will be scheduled. If the Veteran has been assigned to the Relational Agent, the RA will set up the program, explain what the veteran needs to do, then let the veteran use the program. When the veteran finishes the program, the one month appointment for the second session will be scheduled if appropriate.

Protection against Risk

As described above, the potential risks to subjects in this study are of low likelihood and generally not serious. Nevertheless, we have given these risks careful consideration and have developed a plan to ensure that research subjects are protected against them. With respect to ensuring confidentiality and data security,

we will take the following precautions. We will only collect identifiable data when absolutely necessary and scientifically justified. All data will be stored on VA-encrypted laptops and on VA servers behind the VA firewall. Data transmissions between study staff will be minimized, but when necessary, will meet or exceed all standards for encryption and security that are in place for the electronic transmission of Veterans' clinical information, with which the Principal Investigator is familiar. The master list will be stored separately from the coded data.

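### An assistant who knows a Veteran's arm may take that Veteran's 3-month drinking report, because masking is stated only for record abstraction

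*Combined protocol and SAP*

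**What the plan says.** On allocation, the Randomization section states that "the research assistant will randomize Veterans to Treatment as Usual or Treatment as Usual plus Relational Agent Intervention", and the result is visible to that person at once. Recruitment and Informed Consent lists among the assistant's tasks: "randomize the participant, and inform the participant of their assignment". In the agent arm (Relational Agent Intervention-procedure), the assistant enrols the Veteran in the system, introduces the agent, prints the feedback and checks the clinic report for a referral. At session 2, "the research assistant will again set up the computer for the participant and allow them to use the program in privacy, using headphones".

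On outcome collection, the Three-Month Follow-up Interview section says: "The research assistants will conduct the 3-month follow-up interview by telephone with each enrolled study participant". That call "will include completion of the QDS and SIP". It then asks about brief intervention, referral and satisfaction. Of drinking days per week and drinks per drinking day, Dependent Variables says that "each of these measures will be considered separately as primary outcome measures. These variables are measured by the QDS". Under Follow-up Procedures, a team member "will train the research assistants to conduct the in-person and 3 month telephone interviews", so one group is trained for both kinds of interview.

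On masking, the document has one statement, in the section on review of CPRS. It says that the research assistants are blinded to treatment status. It comes straight after the sentence on training them to abstract the record and just before the sentence on oversight of that abstraction. Study Data Management adds that "REDCap allows the assignment of different levels of access privileges and audit trails".

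**The concern.** Veterans cannot be masked to whether they used the agent, so the interviewer is the one part of primary-outcome collection that could be. An interviewer who knows the arm may probe or record differently. A Veteran may also report differently to the person who set up two sessions on cutting down; usual-care Veterans have no such sessions. The more plausible direction is lower reported drinking in the agent arm, but the documents do not establish this.

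The Measures table lists no biomarker or other objective check on drinking. The planned adjustment for baseline would not remove such a bias: the screening QDS is taken before randomisation, so any influence of a known arm enters only at follow-up. Masking is planned for the chart data behind the secondary outcomes, yet none is stated for the primary outcomes, where an interviewer's knowledge has more room to act.

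**Working it through.** **1. Who knows the arm, and who measures the outcome.** Setting the sections side by side:

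- Randomisation and disclosure of the arm: research assistant (Randomization; Recruitment and Informed Consent).
- Sessions 1 and 2, feedback report and clinic report: research assistant (Relational Agent Intervention-procedure).
- 3-month QDS: research assistants (Three-Month Follow-up Interview).
- Rule separating these duties for a given Veteran: none stated.
- Masking of the 3-month caller: none stated.

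The role is shared. Whether one individual does all of this for one Veteran is left open.

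**2. Does the blinding sentence cover the call?** Its position ties it to CPRS abstraction. If it covered everything assistants do, it would contradict the sections in which they randomise and run sessions. Even for abstraction it is hard to square with the rest, because information from the clinic report goes into a CPRS progress note.

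**3. Other routes to the arm.** The System Usability Scale (SUS) and the ECA Questionnaire are scheduled at session 2 for the intervention group only, so their presence in REDCap identifies the arm. Follow-up Procedures also has the team look in CPRS to trace Veterans who are hard to reach, and the progress note is there.

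**4. The plan's own power figures, to fix the scale.** Inputs from Sample Size and Power Considerations: 180 randomised, 20/25/30% loss, hence 72/68/63 per arm (for example 180 × 0.80 / 2 = 72), and alpha 0.05. Assumptions: two-sided test, and medium effect taken as d = 0.5.

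Power ≈ Φ(d·√(n/2) − 1.96). At n = 72: Φ(0.5 × 6 − 1.96) = Φ(1.04) = 0.851. At 68 and 63 per arm the same formula gives 0.830 and 0.801. The exact t-test gives 0.846, 0.825 and 0.795, against the stated 0.84, 0.82 and 0.78. The table is reproduced to within 2 points; a one-sided test (0.91, 0.90, 0.87) does not reproduce it.

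**5. Illustration of what a reporting shift would do.** Suppose there is no true effect and reported drinking differs between arms by b SD because of reporting alone. The size of b is assumed, as the documents give none. Then

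rejection rate = 1 − Φ(1.96 − b·√(n/2)) + Φ(−1.96 − b·√(n/2)).

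- n = 72, b = 0.1: 1 − Φ(1.36) + Φ(−2.56) = 0.087 + 0.005 = 9.2%.
- n = 72, b = 0.2: 1 − Φ(0.76) + Φ(−3.16) = 0.224 + 0.001 = 22.4%.
- Range at 72 per arm: 5.0% (b = 0), 6.0% (0.05), 9.2% (0.1), 22.4% (0.2), 43.7% (0.3).
- Range at 63 per arm: 5.0%, 5.9%, 8.7%, 20.2%, 39.1%.

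These are rates for each primary outcome tested alone. They do not separate a shift due to the interviewer from one due to the Veteran.

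**The case against.** The best reply has five parts.

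- **Same role is not same person.** A reader might infer that whoever randomised a Veteran also makes that Veteran's call. The documents do not say so. They show a shared role and a shared training group, and nothing that rules it out. This limits the wording of the point but does not remove it.
- **The brief-intervention and referral questions need not unmask.** A reader might infer that they reveal the arm. Under Study Arms, usual care already prompts the clinician to give a brief intervention and allows referral, so a yes fits either arm. An answer may disclose the arm if the Veteran mentions the agent. The section also lists the QDS and SIP before these items. It does not state that the listing is a fixed order, and the call script is in an appendix that is not available here.
- **Spare capacity is not shown.** The number of assistants is not given. The plural implies at least two, but they also handle screening, consent, sessions and abstraction, possibly on three campuses. This stands, and the fix is conditional on it.
- **The figures do not measure this defect.** A reader might take 9% and 22% as the harm from unmasked callers, or as the gain from masking them. They are neither: the shift is assumed, and it mixes participant and interviewer knowledge. This stands.
- **The QDS leaves little room for probing, and interviews are monitored.** The QDS is a short summary measure, and Follow-up Procedures provides for checks on interview quality. Both help, but neither masks the caller.

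**Conclusion.** The point holds as a cheap improvement to the design. As written, an assistant who knows the arm may collect the self-reported primary outcomes, and the only masking statement lies elsewhere. That rests on the text and needs no calculation.

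The size of the resulting bias is unknown. An assumed total shift of 0.1 to 0.2 SD would take the per-outcome false-positive rate from 5% to roughly 9% to 22% at 72 per arm (9% to 20% at 63), but the part due to interviewers cannot be isolated. The documents do not support saying that the same individual always follows up a Veteran, that the call necessarily reveals the arm, or that masking would remove reporting bias.

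Separately, the blinding sentence in the CPRS section and the assistants' duties in randomisation and the sessions cannot both stand without qualification.

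**What to change.** - Where at least two assistants are available, assign each 3-month call to one who neither randomised that Veteran nor ran their sessions.
- For that caller, hide in REDCap the allocation field and the SUS and ECA forms from session 2. Have someone else do any CPRS tracing for that Veteran.
- Fix the call order: QDS and SIP first, then the brief-intervention, referral and satisfaction items. Open by asking Veterans not to mention the programme.
- Record any unmasking, and whether it came before or after the QDS.
- Reconcile the blinding sentence in the CPRS section with the sections on randomisation and the agent procedure: say which assistants it covers for which Veterans, and how the progress note is handled.

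Cost: call scheduling, some loss of rapport on the call, and dependence on having at least two assistants. Sample size, alpha and the stated power (0.84/0.82/0.78) do not change. Veterans' own reporting bias remains and should be acknowledged when results are interpreted.
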